5.3 Exclusion criteria

Patients eligible for this study must not meet **any** of the following criteria:

1. Malignant disease, other than that being treated in this study.
2. Patients with the following laboratory values during screening:

- a. Serum creatinine > 1.5 x upper limit of normal (ULN) for age
 - b. Total bilirubin > 1.5 x ULN for age
 - c. Alanine aminotransferase (ALT)/serum glutamic pyruvic transaminase (SGPT) > 3 x ULN for age; aspartate aminotransferase (AST)/serum glutamic oxaloacetic transaminase/SGOT > 3 x ULN for age except in patients with tumor involvement of the liver who must have AST/SGOT and ALT/SGPT ≤ 5 x ULN for age. For the purpose of this study, the ULN for SGPT/ALT is 45 U/L.
3. Systemic antineoplastic therapy or any experimental therapy within 3 weeks before the first dose of LEE011 (6 weeks if prior nitrosourea or bevacizumab).
 4. Radiotherapy within 2 weeks before the first dose of LEE011 (< 6 wks for therapeutic doses of MIBG)
 5. Impairment of gastrointestinal (GI) function or GI disease that may significantly alter the absorption of LEE011 (e.g., ulcerative diseases, uncontrolled nausea, vomiting, diarrhea, malabsorption syndrome, or small bowel resection)
 6. Other severe acute or chronic medical or psychiatric condition or laboratory abnormality that may interfere with the interpretation of study results, and in the judgment of the investigator would make the patient inappropriate for the study.
 7. Major surgery within 2 weeks of the first dose of LEE011. Gastrostomy, insertion of a gastric feeding tube (G-tube), ventriculo-peritoneal shunt, endoscopic ventriculostomy and central venous access are not considered major surgery.
 8. Autologous stem cell transplant following myeloablative therapy within 3 months prior to the first dose of LEE011 or prior allogeneic stem cell transplant at any time. Patients who received stem cell reinfusion following non-myeloablative therapy are eligible once they meet peripheral blood count criteria in Inclusion Criterion #4
 9. Uncontrolled cardiovascular condition, including ongoing cardiac arrhythmias, congestive heart failure, angina, or myocardial infarction within 6 months prior to the first dose of LEE011.
 10. Prior history of QTc prolongation or QTcF > 450 ms on screening ECG.
 11. Left ventricular ejection fraction (LVEF) $< 45\%$
 12. Prior exposure to CDK4/6 inhibitor.
 13. Patients who are currently receiving treatment with agents that are known to cause QTc prolongation in humans. (Refer to [Appendix 6](#)).
 14. Patients who are currently receiving treatment with agents that are metabolized predominantly through CYP3A4/5 and have a narrow therapeutic window and/or agents that are known strong inducers or inhibitors CYP3A4/5 are prohibited. In particular, enzyme-inducing antiepileptic drugs (EIAEDs). (Refer to [Appendix 6](#)).
 15. Pregnant or nursing (lactating) women, where pregnancy is defined as the state of a female after conception and until the termination of gestation, confirmed by a positive hCG laboratory test
 16. Women of child-bearing potential (Refer to [Section 7.2.2.5.4](#)), defined as all women physiologically capable of becoming pregnant (who have attained menarche), **unless** they are using highly effective methods of contraception during dosing of study treatment and for 21 days after stopping study treatment. Highly effective contraception methods include:

[REDACTED]
[REDACTED]
[REDACTED]
[REDACTED]

- Total abstinence (when this is in line with the preferred and usual lifestyle of the patient. Periodic abstinence (e.g., calendar, ovulation, symptothermal, post-ovulation methods) and withdrawal are not acceptable methods of contraception.
- Female sterilization (have had surgical bilateral oophorectomy with or without hysterectomy) or tubal ligation at least six weeks before taking study treatment. In case of oophorectomy alone, only when the reproductive status of the woman has been confirmed by follow up hormone level assessment.
- Male sterilization (at least 6 months prior to screening). The vasectomized male partner should be the sole partner for that patient.
- Use of oral, injected or implanted hormonal methods of contraception or placement of an intrauterine device (IUD) or intrauterine system (IUS), or other forms of hormonal contraception that have comparable efficacy (failure rate <1%), for example hormone vaginal ring or transdermal hormone contraception

In case of use of oral contraception women should have been stable on the same pill for a minimum of 3 months before taking study treatment.

6 Treatment

6.1 Study treatment

For this study, the term “investigational or study drug” refers to LEE011. All dosages prescribed and dispensed to the patient and all dose changes during the study must be recorded on the Dosage Administration Record eCRF.

6.1.1 Dosing regimen

[figure not shown]
LEE011 is provided to investigational sites in capsule, powder in bottle (PIB) or liquid forms for oral use. LEE011 will be taken orally, once a day for 21 consecutive days followed by a 7-day planned break.

LEE011 dose will be scaled by Body Surface Area (BSA). The dose will be adjusted to the nearest 10 or 50 mg (higher or lower) as appropriate. The investigational site staff will inform each patient of their actual daily dose, and this will be recorded on the appropriate eCRF. The actual dose for each patient will be calculated using a BSA conversion as follows:

Actual dose = planned dose level (mg/m²) x individual patient (to nearest 10 or 50 mg, BSA higher or lower as appropriate).

Individual patient BSA will be calculated using their height and weight as per standard site procedure. For the purpose of BSA calculations and potential dose readjustment at subsequent cycles, it is acceptable for the BSA to be calculated up to 7 days in advance of Day 1. Dosage adjustments for changes in BSA in subsequent cycles will be made as per standard site practice (e.g., if the BSA changes by ± 10% from the previous dose calculation).

For capsules, individual doses will consist of the minimum number of capsules possible given the available capsule sizes.

The investigator should instruct the patient to take the study drug exactly as prescribed below. All dosages prescribed and dispensed to the patient, and all dose changes during the study must be recorded on the appropriate eCRF.

6.1.1.1 Alternate dosing regimen of LEE011

No alternate dosing regimen of LEE011 is planned.

6.1.2 LEE011 administration

LEE011 may be administered orally in different ways:

[figure not shown]
1. Capsule: swallow whole or open capsule and pour contents onto semi-solid food or dissolve contents of opened capsule in water or Ora-Sweet (or equivalent) and administer orally or via feeding tube (e.g. nasogastric or gastric)
2. Powder in Bottle (PIB): dissolve powder in water or Ora-Sweet (or equivalent) and administer via feeding tube (e.g. nasogastric or gastric)
3. Liquid formulation.

Since LEE011 shows high solubility across the pH range (> 6 mg/ml at pH 7-9 and > 25 mg/ml at pH 4 or below), the exposure/bioavailability should not be limited by its dissolution rate due to different dosage form of administration. Preliminary in vitro and stability testing support this strategy.

Patients may switch between the different methods of drug administration/formulation depending on clinical status and swallowing abilities. If changes in methods of drug administration/formulation are made during the course of the study and not previously provided to patient, additional PK is recommended as outlined in [Tables 7-4](#) or [7-5](#). PK and safety will be monitored to ensure that there are no major changes related to methods of LEE011 administration. Detailed instructions regarding preparation and administration of LEE011 capsules, PIB and liquid will be supplied separately to patients/caregivers and investigational sites.

LEE011 should be taken as follows:

- Patients should be instructed to take their once-a-day dose at approximately the same time each day.
- On days when blood for PK samples need to be collected prior to taking study drug, the patient should take the dose in the clinic.
- Each daily dose of LEE011 should be taken with water (preferably one cup) and consumed over as short a time as possible unless otherwise instructed.
- Patients taking capsules should be instructed to swallow capsules whole and to not chew or open them unless otherwise instructed.
- Patients should prepare the dose as described in the Instructions for Use (to be supplied to Investigator sites separate to this protocol).
- Ribociclib can be administered with or without food; however dietary habits around the time of dosing should be as consistent as possible throughout the study.

- On days of PK/PD sampling, every effort must be made to capture the time of any vomiting within 4 hours of drug administration.
- If vomiting occurs during the course of the treatment, then no re-dosing of the patient is allowed before the next scheduled dose.
- Any doses that are missed (not taken within 6 hours of the intended time) should be skipped and should not be replaced or made up on a subsequent day.
- Patients should inform the investigational site staff of any missed or delayed doses
- Patients must avoid consumption of grapefruit products, pummelos, star-fruit, Seville oranges or products containing the juice of each during the entire study and preferably 7 days before the first dose of study medications, due to potential CYP3A4 interaction with the study medications. Orange juice is allowed.

6.1.3 Treatment duration

Patients may continue to receive treatment with LEE011 until disease progression, occurrence of unacceptable toxicity that precludes any further treatment, if treatment is discontinued at the discretion of the investigator, the patient withdraws consent or the patient is enrolled in another Novartis study that can continue to provide LEE011. Patients who have localized disease progression but have evidence of clinical benefit may continue treatment with LEE011 after discussion with Novartis and investigator. Patients who continue on treatment after localized disease progression must discontinue treatment if there is subsequent systemic disease progression.

6.2 Dose escalation guidelines

6.2.1 Starting dose for the dose escalation part

The first cohort of patients in this trial will be treated with a dose of 280 mg/m²/d, which is 80% of the current well tolerated dose (600 mg/d) in the ongoing adult study [CLEE011X2101] divided by the average adult body surface area (BSA) of 1.72 m². Table 6-1 describes the starting dose and the dose levels that may be evaluated during this trial.

Table 6-1 Provisional dose levels

Dose level	Proposed daily dose*	Increment from previous dose	Corresponding adult dose level
-1 [°]	210 mg/m ²	-25%	360 mg/d
1 (starting dose)	280 mg/m ²	(starting dose)	480 mg/d
2	420 mg/m ²	50%	720 mg/d
3	630 mg/m ²	50%	1080 mg/d

This table is intended only as a guide. Values in table are examples and actual doses may vary.

* Additional dose levels may be added during the course of the study. Cohorts may be expanded at any dose level below MTD in order to better understand safety, PK or PD.

[°] Dose level -1 is a dose level that may be evaluated if the starting dose level is not well tolerated

Since the adult MTD has not been established, LEE011 doses higher than 630 mg/m² may be evaluated depending on the data from the adult Ph1 study and observed safety, PK and PD.

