The MTD of LEE011 for the 3 weeks on/1 week off schedule was determined to be 900 mg. Continuous dosing with LEE011 at 600 mg was also evaluated. This dosing regimen was not well tolerated and will therefore not be pursued further. The study continues to explore intermediate doses to establish the RDE and further assess the safety, tolerability, and preliminary anti-tumor activity of LEE011.

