2.3 Rationale for dose and regimen selection

The MTD of LEE011 for the 3 weeks on/1 week off schedule is 900 mg. The RDE in adults will most likely be 600 mg on the same regimen. The dose from the adult Phase 1 study that will be used to calculate the starting dose in children is 600 mg/d. This is based upon review of the safety, tolerability, and PK observed at this dose level and higher. At the 600 mg/d dose in adults, LEE011 was well tolerated with an acceptable safety profile. At this dose, systemic exposures corresponding to efficacy in preclinical models was observed. On target toxicity, neutropenia, was seen but not dose-limiting. Therefore, using the 600 mg/d dose from the adult study for calculating the starting dose in children offers a high probability of beginning at an active dose and a low probability of excessive toxicity.

The first cohort of children in this trial will be treated with a dose of 280 mg/m²/d, which is 80% of the current well tolerated dose (600 mg/d) in the ongoing adult study [CLEE011X2101] divided by the average adult body surface area (BSA) of 1.72 m². Refer to Section 6.2.1 for details.

In adults, LEE011 is dosed once daily orally, and the T_{1/2}, acc ranges from 24.2 to 40 hours. This supports once daily dosing in children. LEE011 will be dosed once a day for 21 consecutive days followed by a 7-day planned break as part of each 28-day cycle of treatment consistent with the regimen used in [CLEE011X2101].

3 Objectives and endpoints

Objectives and related endpoints are described in Table 3-1 below.

[figure not shown]

Table 3-1 Objectives and related endpoints

Objective	Endpoint	Analysis
Primary		
Determine the MTD and/or RDE of LEE011	Incidence rate of DLTs in Cycle 1	Refer to Section 10.4 .
Secondary		
(1) Characterize the safety and tolerability of LEE011	(1) AEs and serious adverse events (SAEs), changes in laboratory values and electrocardiograms (ECGs).	Refer to Section 10.5 .
(2) Characterize the PK of LEE011 and any clinically significant metabolites that may be identified	(2) Plasma concentration time profiles of LEE011, PK parameters, including but not limited to AUCtau, Cmax, Tmax, CL/F, accumulation ratio (Racc), and T1/2,acc	
(3) Assess the anti-tumor activity of LEE011	(3) Overall response rate (ORR), duration of response (DOR), and time to progression (TTP) per RECIST 1.1. In addition, for neuroblastoma, response by INRC. In addition, for primary CNS tumors, response by RANO Criteria.	
Exploratory		

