6.2.2 Guidelines for dose escalation and determination of (MTD/ RDE)

For the purposes of dose escalation decisions, 3 to 6 patients will be enrolled in successive cohorts. The first cohort will be treated with the starting dose of 280 mg/m²/d. Patients must complete a minimum of 1 cycle of treatment with the minimum safety evaluation and drug exposure or have had a DLT within the first cycle of treatment to be considered evaluable for dose escalation decisions. Dose escalation decisions will occur when the cohort of patients has met these criteria. Dose escalation decisions will be made by Investigators and Novartis study personnel. Decisions will be based on a synthesis of all relevant data available from all dose levels evaluated in the ongoing study including safety information, DLTs, all CTCAE grade \geq 2 toxicity data during Cycle 1, and PK, data from evaluable patients. PK data from patients will be made available on an on-going basis throughout the study and dosing will be adapted accordingly. The recommended dose for the next cohort of patients will be guided by the BLRM with EWOC principle.

The adaptive Bayesian methodology provides an estimate of all dose levels of LEE011 that do not exceed the MTD and incorporates all DLT information at all dose levels for this estimation. In general, the next dose will have the highest chance that the DLT rate will fall in the target interval (16-33%) and will always satisfy the EWOC principle. In all cases, the dose for the next cohort will not exceed a 100% increase from the previous dose. Smaller increases in dose may be recommended by the Investigators and Sponsor upon consideration of all of the available clinical data.

[figure not shown]
If the first 2 patients in a previously untested dose level experience a DLT, the next cohort will be opened at the next lower dose level or an intermediate dose level (see [Table 6-1](#), [Appendix 7](#)). However, if the first 2 patients in a new cohort at a previously tested dose level experience a DLT, further enrollment to that cohort will stop and the BLRM will be updated with this new information. Re-evaluation of the available safety, PK, and PD data will occur.

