6.2.2.1 Implementation of dose escalation decisions

To implement dose escalation decisions, the available toxicity information (including AEs and laboratory abnormalities that are not DLTs), the recommendations from the BLRM, and the available PK and PD information will all be evaluated by the Investigators and Novartis study personnel (including the study physician and statistician) during a dose decision meeting by teleconference. Drug administration at the next higher dose level may not proceed until the investigator receives written confirmation from Novartis indicating that the results of the previous dose level were evaluated and that it is permissible to proceed to a higher dose level.

Dose escalation will continue until MTD and/or the RDE is reached. The dose for the expansion part will either be the MTD, or a lower dose that is determined to be the RDE.

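### Does the remark in Section 6.2.1 that no adult MTD exists undermine the option to go above 630 mg/m²?

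*Protocol*

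**What the plan says.** Section 6.2.1 (text below Table 6-1) gives its reason as "Since the adult MTD has not been established" and then says that doses above 630 mg/m² "may be evaluated depending on the data from the adult Ph1 study and observed safety, PK and PD". The notes to the same table describe it as a guide with example values and say that levels may be added during the study.

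Section 1.2.1.2 states: "The MTD of LEE011 for the 3 weeks on/1 week off schedule was determined to be 900 mg". It adds: "The study continues to explore intermediate doses to establish the RDE". Section 2.3 repeats the first point, "The MTD of LEE011 for the 3 weeks on/1 week off schedule is 900 mg", and says of the other quantity: "The RDE in adults will most likely be 600 mg on the same regimen". All three sections are current text and refer to the same adult study, CLEE011X2101.

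Escalation is governed elsewhere. Section 6.2.2 says: "In all cases, the dose for the next cohort will not exceed a 100% increase from the previous dose". Section 6.2.2.1 says: "Drug administration at the next higher dose level may not proceed until the investigator receives written confirmation from Novartis" (the confirmation must state that the previous level was evaluated and that a higher level is permissible). Section 10.4.2 excludes any dose with more than a 25% posterior chance that its DLT rate exceeds 0.333.

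**The concern.** Section 6.2.1 says one thing about the adult MTD and two other sections say the opposite. The sentence is also the only reason that Section 6.2.1 offers for going beyond its highest listed level, in a study of children. A reader of that section alone would think that no adult MTD was known, when the protocol reports one that converts to less than the top listed level.

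The adult figure matters on the protocol's own terms: Appendix 7 expects the cycle 1 DLT probability at a given mg/m² dose to resemble that at the corresponding adult flat dose. If escalation above 630 mg/m² really depended on the absence of an adult MTD, that option would lose its basis. The question is whether anything does depend on it.

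**Working it through.** **Inputs.** Adult MTD 900 mg (Sections 1.2.1.2 and 2.3). Conversion by average adult BSA of 1.72 m², reference dose 600 mg/d and factor 80% (Sections 2.3 and 6.2.1). Dose levels and adult equivalents from Table 6-1. Scenario 11 from Table 14-15.

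**Step 1: reproduce the protocol's figures.**
- Starting dose: 0.80 × 600 / 1.72 = 279.1 mg/m² (stated 280).
- Adult equivalent = dose × 1.72:
  - 210 gives 361 (stated 360)
  - 280 gives 482 (480)
  - 420 gives 722 (720)
  - 630 gives 1084 (1080)

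The conversion scale is confirmed.

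**Step 2: place the reported adult MTD on that scale.** 900 / 1.72 = 523 mg/m², between level 2 (420) and level 3 (630). From the table's own figures, 1080 / 900 = 1.20, so the disputed sentence covers only doses above about 1.2 times the reported adult MTD. Varying the BSA from 1.6 to 2.0 m² (an assumed range) moves 523 to between 562.5 and 450 mg/m², still below 630. The contradiction is genuine and does not turn on rounding.

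**Step 3: look for anything that uses the clause.**

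| Element | Where | Refers to the adult MTD being unknown? |
|---|---|---|
| Adding dose levels | Notes to Table 6-1 | No |
| Listing 630 mg/m² (1080 mg/d) | Table 6-1 | No; it already exceeds 900 mg/d |
| Conditions on doses above 630 mg/m² | Rest of the same sentence | No; adult data and observed safety, PK and PD |
| Size of increment | Section 6.2.2 | No; 100% cap |
| Overdose control | Section 10.4.2 | No; 25% limit on the chance that the DLT rate exceeds 0.333 |
| Release of the next level | Section 6.2.2.1 | No; written sponsor confirmation |
| Declaring the MTD or RDE | Section 6.2.2 | No; patient counts, posterior probability and clinical review |

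No section makes the adult MTD a ceiling, and none makes its absence a condition.

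**Step 4: how a dose above 630 mg/m² would be reached.** Scenario 11 in Table 14-15 has no DLTs in 3 patients at each of 280, 420 and 630 mg/m², and gives 850 mg/m² as the next dose. The increment is 850/630 − 1 = 35%, against a cap of 100%. The stated overdose probability is 7.2%, against a limit of 25%. The step follows from the model and the listed rules, and the disputed clause plays no part.

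**Step 5: try the repairs.** Replace MTD with RDE in the clause, reword the premise, or delete it. In each case the permission, its conditions and every row of the table above stay as they are.

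**The case for a change.** The strongest reply is that safeguards show how escalation is controlled, not why it may go so far. The notes to Table 6-1 give permission without a reason, so the one reason in Section 6.2.1 is contradicted elsewhere. The range is not remote either. The adult 1200 mg cohort converts to 1200/1.72 = 698 mg/m², inside the range that the sentence opens, and Section 1.2.1.2 reports two DLTs there with three patients treated, and grade 1 or 2 QTc prolongation in all three. The 850 mg/m² of scenario 11 converts to 850 × 1.72 = 1462 mg/d, above every adult dose listed in that section.

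The criticism of the wording stands. The protocol treats MTD and RDE as different quantities, and if RDE was meant the sentence should say so. What does not stand is the inference that the option is left without support. The adult results are set out in the same protocol, and the sentence itself tells the decision makers to take the adult study into account. Section 2.1 also gives a general rationale, namely that children tolerate toxicity at least as well as adults and that paediatric safety and PK data will steer escalation. Whether that rationale is sufficient is a clinical judgement, on which this note takes no view.

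**Conclusion.** This is a clerical slip. Section 6.2.1 conflicts with Sections 1.2.1.2 and 2.3, most likely because its wording was not revised when the adult experience was updated. The three passages must be reconciled so that they agree on the adult MTD. That is an editorial correction to one clause. It alters no dose level, escalation rule, model input, threshold, patient number or analysis, so no change to the plan follows.

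The conclusion rests on two readings. The first is that the notes to Table 6-1 are a free-standing permission to add levels. The second is that the limits in Sections 6.2.2, 6.2.2.1 and 10.4.2 apply at every step, including above 630 mg/m². Both follow from the text. Most of the derivation of the prior in Appendix 7 is blacked out, so how the adult data enter the model cannot be checked, and nothing here relies on it. The practical effect is smaller still because SAP Section 2.5 records that the MTD/RDE was determined before enrolment was halted and plans no MTD analysis for the final report. Nothing here says which dose or limit is right.
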